5.13. Summary of Analyses of Other Efficacy and Exploratory Endpoints

Change from baseline at each visit in total “asleep” time based on the 2 day average of Hauser diary will be analyzed in a similar way as the analyses described in [Section 5.12](#) to explore the pattern of sleep time. In addition, change from baseline in the MDS UPDRS Part II+III score (all time points) will be explored using the same analysis method.

5.14. Interim and Final Analysis

Given the uncertainty on the assumption of a population standard deviation of 2.5 in the primary endpoint in designing the sample size of this study, an interim analysis is planned to determine whether the variability in the current study population will require a sample size re-estimation.

After approximately 67% of the subjects (248 of 368 planned) have completed the study or discontinued prematurely, an interim analysis of the primary efficacy endpoint only will be conducted by an independent Interim Analysis Review Committee (IARC), which may make a recommendation to increase the overall sample size up to a maximum of 528 subjects. The modification to the sample size will be based on interim estimate of nuisance parameter from analyses that utilize treatment assignment information as described in Section V.B of Adaptive

Designs for Clinical Trials of Drugs and Biologics Guidance for Industry ([FDA, 2019](#)). The approach generally has limited impact on the overall type I error rate and minimize the risk of operational bias, provided the integrity of blind is rigorously maintained. Details of the sample size re-estimation algorithm and the rules for the IARC are provided in [Section 9.1](#).

A final analysis will be conducted once the last subject completes or discontinues the study, and the resulting clinical database has been cleaned, quality checked, the pre-analysis meeting has occurred, and the database has been locked.

5.15. Safety Analyses

All safety analyses will be performed on the Safety analysis set. Should any subjects receive a treatment other than their randomized treatment, the treatment as received will be used in the safety presentation.

5.15.1. Adverse Events

Adverse events will be mapped to a Medical Dictionary for Regulatory Activities (MedDRA) version 26.1 or higher preferred term and system organ class. If a subject experiences multiple events that map to a single preferred term, the greatest intensity and strongest investigator assessment of relation to IMP will be assigned to the preferred term for the appropriate summaries. Events with missing intensity or relationship will be classified as outlined in [Section 3.2](#). Missing onset dates will be imputed as previously outlined in [Section 3.2](#) as required to determine treatment-emergent events.

Summaries of treatment-emergent AEs will include any AEs reported beginning with the initiation of study drug on Day 1 through end of reporting period specified in the protocol post the last dose of IMP. The occurrence of TEAEs will be summarized by treatment group using preferred terms, system organ classes, and intensity. Separate summaries of treatment-emergent serious adverse events (TESAEs), TEAEs related to IMP, AESIs (including AEs related to abuse potential and AEs involving medication handling irregularities), and events leading to the discontinuation of IMP will be generated respectively. A summary of AEs by treatment phase and by dose at event onset will also be presented. All adverse events reported will be listed for individual subjects showing both verbatim and preferred terms. All adverse events that occurred prior to the initiation of study treatment or after the protocol-specified reporting period post the last dose of IMP will be excluded from the summary tables but will be included in the listings.

In addition, TEAEs rate per 100 person-years of exposure (PYE) will be summarized by treatment group using system organ class and preferred term. TEAEs leading to dose reduction will be summarized by treatment group using preferred terms and system organ classes.

Furthermore, TEAEs with $\geq 2\%$ incidence in the treatment group and a greater incidence than the placebo group will be summarized by treatment group using preferred term in descending order of the incidence in the tavapadon group. The most common TEAEs in the tavapadon group, defined as an incidence $\geq 5\%$ and greater than 2 times of the incidence in the placebo group, will also be summarized by treatment group using preferred term in descending order of the incidence in the tavapadon group.

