1 PROTOCOL SUMMARY

1.1 Synopsis

Sponsor Name: Cerevel Therapeutics, LLC

Name of Investigational Medicinal Product: Tavapadon

Protocol Title: A Phase 3, Double-Blind, Randomized, Placebo-Controlled, Parallel-Group, Flexible-Dose, 27-Week Trial to Evaluate the Efficacy, Safety, and Tolerability of Tavapadon as Adjunctive Therapy for Parkinson's Disease in Levodopa-Treated Adults With Motor Fluctuations (TEMPO-3 Trial)

Short Title: Flexible-Dose, Adjunctive Therapy Trial in Adults With Parkinson's Disease With Motor Fluctuations

IND Number: 118,647

EudraCT Number: 2019-002951-40

Trial Phase: 3

Indication: Parkinson's disease

Rationale: Tavapadon (PF-06649751, CVL-751) is a partial agonist of the dopamine D1-like receptors (D1Rs), with high specificity for the D1 and D5 receptor subtypes (D1/D5), which is being developed as a treatment for Parkinson's disease (PD). The efficacy, safety, and tolerability of tavapadon in Phase 1b and 2 trials support its potential as the first partial agonist therapy in an important new dopamine receptor-selective mechanism for treatment of PD symptoms. By targeting the D1R subtype, tavapadon aims to improve motor control symptoms while minimizing adverse events (AEs) that may be mechanistically linked to D2/D3 dopamine receptor agonists (notably, dose-limiting hypotension, impulse control disorders, sleep disorders, and, potentially, some forms of hallucinations). This trial is designed to further define and confirm the magnitude of efficacy and the risk/benefit profile of tavapadon over the target dose range of 5 to 15 mg once daily (QD).

Objectives and Endpoints:

The objectives and efficacy, safety, and pharmacokinetic (PK) endpoints of the trial are summarized in [Table 1](#).

Table 1 Objectives and Endpoints

Objectives	Endpoints
Efficacy	

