8.4.6 Adverse Events of Special Interest

8.4.6.1 Adverse Events Potentially Related to Abuse

A key objective of the Abuse Potential Monitoring Plan (APMP) is to monitor for instances of abuse or diversion of the trial medication and other psychoactive substances.

In addition to monitoring for irregularities in medication handling, AEs that may be suggestive of a developing abuse issue will also receive special attention. As part of the APMP, medication handling irregularities (MHIs) must be reported, and AEs related to

abuse potential and AEs involving MHIs must be reported as events subject to additional monitoring (ESAMs), with detailed narratives.

Investigators and site staff at each trial site will be trained on reporting potentially abuse related AEs (eg, recording a description of the event in the subject's own words in the source documents as well as the eCRF, in addition to the clinical term, and to be aware that a subject's report may encompass more than one event and that these should be recorded separately). The investigators will be provided with examples of potentially abuse-related AEs and trained on how to handle such events (eg, additional monitoring).

While the investigators will be provided with examples of AE terms as a guide during trial conduct, the analysis of potentially abuse-related AEs will be based on a search by the sponsor of all relevant Medical Dictionary for Regulatory Activities (MedDRA) terms, all verbatim terms, and any open text fields within the AE data to identify text strings suggestive of abuse potential, consistent with US Food and Drug Administration (FDA) guidance (Guidance for Industry: Assessment of Abuse Potential of Drugs, January 2017).

Complete details, including documenting and reporting procedures, examples of potentially abuse-related terms and guidance for the training of investigators and trial site staff are provided in the APMP.

8.4.6.2 *Abnormal Liver Function Tests*

The finding of an elevated value for alanine aminotransferase (ALT) or aspartate aminotransferase (AST) of $>3 \times$ the upper limit of normal (ULN) in combination with either an elevated value for total bilirubin $>2 \times$ ULN or clinical jaundice in the absence of cholestasis or other causes of hyperbilirubinemia is considered to be an indicator of severe liver injury. Therefore, investigators must report the occurrence of either of the following as AESI to the sponsor with 24 hours:

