3.2.3.1. Adverse Event of Special Interest (AESI)

For this study, any AEs related to abuse potential, abnormal liver function tests with a value $>3 \times$ ULN for ALT or AST and $>2 \times$ ULN for total bilirubin within the same visit, a value of $>3 \times$ ULN for ALT or AST and clinical jaundice, an AE leading to the discontinuation of IMP or from the study will be considered AESIs. These events will be noted by the investigator in the ADVERSE EVENTS eCRF

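### The 2% and 5% TEAE tables work on single preferred terms, and no grouped AE count is planned for the four harms the protocol says tavapadon aims to minimise; the gap is clearest for hallucinations

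*SAP*

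**What the plan says.** SAP 5.15.1 plans a full TEAE table: "The occurrence of TEAEs will be summarized by treatment group using preferred terms, system organ classes, and intensity". It then adds two tables with cut-offs. The first takes terms with at least 2% "incidence in the treatment group and a greater incidence than the placebo group will be summarized by treatment group using preferred term". The second, labelled as the most common TEAEs, takes terms with at least 5% on tavapadon "and greater than 2 times of the incidence in the placebo group, will also be summarized by treatment group using preferred term". Neither cut-off table has a system organ class level or a grouped category.

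The rationale in Protocol 1.1 says tavapadon aims to improve motor control while minimising AEs linked to D2/D3 agonists: "notably, dose-limiting hypotension, impulse control disorders, sleep disorders, and, potentially, some forms of hallucinations". Protocol 2.1 repeats this.

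The AE groupings that are planned lie elsewhere. SAP 5.15.1 gives separate summaries for "AESIs (including AEs related to abuse potential and AEs involving medication handling irregularities" events. SAP 3.2.3.1 defines AESIs as abuse-related events and certain liver-test findings, and adds that "an AE leading to the discontinuation of IMP or from the study will be considered AESIs". The only multi-term search in either document is for abuse-related AEs, "based on a search by the sponsor of all relevant Medical Dictionary for Regulatory Activities (MedDRA) terms" (Protocol 8.4.6.1).

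Several analyses outside the AE tables bear on these harms:
- **Hypotension:** counts of subjects meeting supine and orthostatic blood-pressure criteria (SAP 5.15.6.1).
- **Sleep:** ESS categories and an MMRM on the ESS total (SAP 5.15.2), and diary sleep time (SAP 5.13).
- **Impulse control:** QUIP-RS scores and an MMRM on the ICD score (SAP 5.15.3).
- **Hallucinations:** none.

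**The concern.** One clinical harm can be coded to several preferred terms. Each term is then compared with the cut-off alone, and the harm may reach 5% in total while no term does. Term rows cannot simply be added, because a subject may appear in more than one. A system organ class total does not help either, since it mixes the harm with unrelated events.

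The documents do not show how events will be coded, so splitting is a possibility and not a documented fact. Their own wording makes it plausible. Protocol 2.3 speaks separately of orthostatic blood pressure changes and of asymptomatic hypotension. It also lists sleep disorder among the AEs that led to discontinuation, while Protocol 8.5 lists abnormal dreams among the commonest TEAEs.

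What is at stake is presentation. A table of most common events tends to be the one carried forward, and it could omit an excess of a harm that the programme names as one to be minimised. The trial would also have no prespecified incidence by arm for that harm as an AE. If grouping is left until after unblinding, the choice of terms can be challenged as data-driven whichever way the result falls.

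**Working it through.** **Inputs.** 184 per group (SAP 1.2), with a maximum of 528, or 264 per group (Protocol 9.5, SAP 5.14). The two display rules come from SAP 5.15.1. The safety set requires at least one dose, so its size may be slightly below 184 per group.

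**The plan's own figure.** The documents give no AE calculation; 184 enters only as the denominator. It reproduces: n = 2 × 2.5² × (1.969 + 1.282)² / 1² = 132.04, so 133 evaluable per arm. Then 133/0.73 = 182.2, so 183 per arm and 366 in total, against 368 stated. A two-sample t-test with 135 per arm gives 90.4% power, as in SAP Table 5.

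**Step 1: cut-offs as whole subjects, 184 per arm.**
- 2% rule: 0.02 × 184 = 3.68, so at least 4 subjects in one term.
- 5% rule: 0.05 × 184 = 9.2, so at least 10 subjects in one term.

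**Step 2: how much can be hidden, with no incidence assumed.** With k terms and one term per affected subject, the largest total with no term qualifying is k × (cut-off − 1).
- 5% rule, k = 3: 3 × 9 = 27 subjects, 27/184 = 14.7%.
- 2% rule, k = 3: 3 × 3 = 9 subjects, 9/184 = 4.9%.
- At 264 per arm the cut-offs are 14 and 6 subjects, and three terms can hide 39 (14.8%) and 15 (5.7%).

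This is a bound: it shows what is possible, not what is likely.

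**Step 3: how likely, under assumed rates and splits.** The documents give neither. Each setting used 200,000 simulated trials, 184 per arm, with the group risk divided over three terms. The chance that at least one term qualifies is compared with the same rule applied to the group total.

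| Assumed rate, tavapadon v placebo | 5% table: group | 5% table: any term, even split | 5% table: any term, 60/25/15 | 2% table: group | 2% table: any term, even split |
|---|---|---|---|---|---|
| 4% v 1% | 20% | 0.1% | 1.4% | 92% | 55% |
| 6% v 2% | 58% | 1.3% | 12.5% | 97% | 88% |
| 8% v 2% | 86% | 8% | 38% | 99.6% | 98% |
| 10% v 3% | 86% | 24% | 61% | 99.7% | 99.7% |

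**Step 4: exact check of the 6% v 2% row.** Under an even split each term has risk 2% on tavapadon and 0.67% on placebo. From the binomial distribution, the chance that one term has at least 10 of 184 and more than twice the placebo count is 0.0042. For three terms, treated as independent, 1 − (1 − 0.0042)³ = 1.3%. Under 60/25/15 the largest term (3.6% v 1.2%) gives 12.4%, and the other two add almost nothing. The group gives 57.7%. These agree with the simulation.

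**Step 5: the larger trial.** At 264 per arm, 6% v 2% gives 64% for the group, against 0.3% (even split) and 9.5% (60/25/15) for any term. A sample size increase does not remove the gap.

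**The case against.** The strongest case against is that this concerns two supplementary displays.

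- **Nothing is removed.** The full TEAE, exposure-adjusted rate and dose-reduction tables use organ class and preferred term with no cut-off, and every AE is listed. This stands. A reader might infer that such harms could vanish from the AE reporting; the documents do not support that.
- **Three harms are measured in other ways.** A reader might infer that no subject-level count exists for any of them. That is wrong: SAP 5.15.6.1 counts subjects meeting blood-pressure criteria, and SAP 5.15.2 gives the percentages with ESS of at least 10 and at least 18. The cover is partial. ESS measures daytime sleepiness and not other sleep disorders, QUIP-RS is summarised as scores, and visit readings miss hypotension between visits.
- **No claim is tied to the 5% table.** A reader might infer that the trial would seem to bear out its D2/D3 rationale through coding alone. The rationale states an aim, the formal hypotheses cover only on and off time, and the ESS, QUIP-RS and blood-pressure data stand regardless of AE coding.
- **The probabilities rest on assumptions.** They do, and an even split is the severest case: moving to 60/25/15 raises 1.3% to about 12%. Protocol 10.3.1 and 10.3.3 also ask for one AE per underlying pathology and for a diagnosis where possible. That limits several terms in one subject, but not different terms across subjects.
- **The 2% table usually catches the harm.** At 6% v 2% it does so in 88% of trials, against 97% for the group. It then shows terms of about 2% each, not the 6%.

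**Conclusion.** The point holds in a limited form. Both cut-off tables are defined on single preferred terms, and no grouped AE count is planned for the four named harms. A harm spread over terms can therefore miss the 5% table: up to 27 of 184 subjects (14.7%) over three terms by arithmetic alone. Under the assumed 6% v 2%, some term qualifies in 1% to about 12% of trials, against 58% for the group. The 2% table is materially affected only at low rates (4% v 1%: 55% against 92%) or wide splits.

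The size depends on assumed incidences and on three-term splits with one term per affected subject. The effect is on which events are displayed as common and on the lack of an incidence per harm; no data or formal test is affected. The gap is partial for hypotension, impulse control and sleep, and clearest for hallucinations. This is a cheap improvement to make, not a flaw in the main safety reporting.

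**What to change.** In SAP 5.15.1, before unblinding:

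1. Fix preferred-term lists for hallucinations, hypotension, impulse control disorders and sleep disorders.
2. Count each subject once per group.
3. Report incidence by arm and the difference with a 95% CI for every group, with no incidence cut-off. Applying the 5% rule to groups would still miss a 6% v 2% harm in about 42% of trials (100% − 58%).
4. Leave the preferred-term tables unchanged and place the grouped table beside them.

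The interval should be read as descriptive. At 6% v 2% with 184 per arm, the standard error is √(0.06 × 0.94/184 + 0.02 × 0.98/184) = 0.020, so the 95% CI runs from about 0 to 8 percentage points.

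The cost is a paragraph of SAP text, four short lists and one table from data already coded. The downside is that choosing terms needs medical judgement, which is why the lists must be fixed while the trial is blinded.

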5.15.2. Epworth Sleepiness Scale (ESS)

The ESS individual questions and total score and corresponding changes from baseline will be summarized by treatment group and study visit. The percentage of subjects with sleepy (10 or more) and very sleepy (18 or more) scores will also be summarized. ESS individual question score as well as the total score will be presented in a listing. The ESS total score will also be analyzed using the same method (MMRM analysis) described in [Section 5.9.2](#) to explore any treatment difference in sleepiness.

5.15.3. Questionnaire for Impulsive-Compulsive Disorders in Parkinson Disease Rating Scale (QUIP-RS)

The QUIP-RS component scores (Gambling, Sex, Buying, Eating, Hobbyism-Punding, PD Medication Use), total ICD score, and total score and corresponding changes from baseline will be summarized by treatment group and study visit. QUIP-RS individual data will be presented in a listing. The total ICD score will also be analyzed using the same method (MMRM analysis) described in [Section 5.9.2](#) to explore any treatment difference in impulsive-compulsive behaviors.

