2 INTRODUCTION

2.1 Trial Rationale

Tavapadon (PF-06649751, CVL-751) is a partial agonist of the dopamine D1-like receptors (D1Rs), with high specificity for the D1 and D5 receptor subtypes (D1/D5), which is being developed as a treatment for Parkinson's disease (PD). Efforts to develop selective D1R agonists have been ongoing for decades, in part, because of their clear potential to produce robust efficacy through selective stimulation of the direct pathway. Mechanistic evidence also suggests that selective and partial activation of D1Rs may avoid some of the limiting side effects of the D2/3 agonist or dopamine replacement therapies.

The efficacy, safety, and tolerability of tavapadon in Phase 1b and 2 trials support its potential as the first partial agonist therapy in an important new dopamine receptor-selective mechanism for treatment of PD symptoms. By targeting the D1R subtype, tavapadon aims to improve motor control symptoms while minimizing adverse events (AEs) that may be mechanistically linked to D2/D3 dopamine receptor agonists (notably, dose-limiting hypotension, impulse control disorders, sleep disorders, and, potentially, some forms of hallucinations).

This prospective, Phase 3, multicenter, multinational, randomized, double-blind, placebo-controlled, parallel-group, 27-week trial will evaluate the efficacy, safety, tolerability, and pharmacokinetics (PK) of flexible doses of tavapadon (5 mg to 15 mg once daily [QD]) as adjunctive therapy for PD in levodopa (L-Dopa)-treated adults with motor fluctuations to further define and confirm the magnitude of efficacy and risk/benefit profile of this target dose range.

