5.2 Exclusion Criteria

Subjects are excluded from the trial if any of the following criteria apply:

Parkinson's Disease Diagnosis	
1.	Subjects with a history or clinical features consistent with essential tremor, atypical or secondary parkinsonian syndrome (including, but not limited to, progressive supranuclear palsy, multiple system atrophy, cortico-basal degeneration, or drug-induced or poststroke parkinsonism).
2.	Subjects with a history of nonresponse or insufficient response to L-Dopa at therapeutic dosages.
3.	Subjects who have had previous surgical intervention (eg, deep brain stimulation) for PD or for whom such a procedure is planned or anticipated during the trial period.

Medical History	
4.	
Subjects with an acute or chronic, clinically significant medical or psychiatric condition, cognitive impairment, or laboratory abnormality that might increase the risk associated with trial participation or administration of trial treatment or interfere with the interpretation of the trial results or that, in the judgment of the investigator, would make the subject inappropriate for entry into this trial.
 
Medical conditions that are minor or well controlled may be considered acceptable if the condition does not expose the subject to an undue risk of a significant AE or interfere with the assessments of safety or efficacy during the course of the trial. Subjects with symptoms of anxiety or depression that are not debilitating and that are stable or adequately controlled with non-prohibited medication are considered acceptable. The medical monitor should be contacted in any instance where the investigator is uncertain regarding the stability of a subject's medical conditions(s) and the potential impact of the condition(s) on trial participation.

5.	Subjects with a history or current diagnosis of a clinically significant impulse control disorder (Disruptive, Impulse Control, and Conduct Disorder per DSM-5) (American Psychiatric Association, 2013).
6.	Subjects with the presence of or history of brain tumor, hospitalization for severe head trauma, epilepsy (as defined by the International League Against Epilepsy), or seizures.
7.	Subjects with a history of psychosis or hallucinations within the previous 12 months.

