1.2. Sample Size Considerations

A sample size of 184 subjects per group (total, 368 subjects) will provide at least 90% power to detect a change in the primary outcome measure (change from baseline in "on" time without troublesome dyskinesia) of 1 hour with a standard deviation of 2.5, a 2 sided alpha level = 0.049, and assuming a 27% dropout rate. The sample size calculation was based on a two-sample t-test with equal variance.

Given that the assumptions for the sample size were based on a preliminary study of limited sample size using a different dosing schedule, it is unknown if the assumption of a standard deviation of 2.5 is a reasonable estimate of the population variability and appropriate for this study as designed. To this end, an interim analysis of the primary efficacy endpoint will be included to assess the adequacy of the overall sample size relative to achieving the study objectives. [Section 9.1](#) provides further detail on the conduct of the interim analysis. Should the interim analysis indicate a requirement of sample size increase per pre-defined decision rule ([Section 9.1](#)) to maintain statistical power, Cerevel will extend enrollment to achieve the required sample size.

In the event of higher than anticipated early terminations due to COVID-19 or other reasons, Cerevel may also extend enrollment in order to maintain the planned statistical power.

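### SAP 5.15.3 plans no by-arm count of subjects with a new or worsened impulse-control problem on the QUIP-RS, and its one test, on mean total ICD score, has low to moderate power for harm in a minority

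*SAP*

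**What the plan says.** SAP 5.15.3 summarises the QUIP-RS component scores, the total ICD score and the total score, with changes from baseline, by arm and visit. Individual data are listed. It adds one model: "The total ICD score will also be analyzed using the same method (MMRM analysis) described in" the primary efficacy section (SAP 5.9.2). The stated purpose of that model is "to explore any treatment difference in impulsive-compulsive behaviors". SAP 5.1 defines descriptive statistics to include the median, quartiles, minimum and maximum. Protocol Table 10 plans descriptive statistics only for this scale.

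SAP 3.2.1 scores each of four ICDs and three related disorders from 0 to 16 and gives the overall total as 0 to 112. It does not define the total ICD score. If it is the sum of the four ICDs, the range is 0 to 64.

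Other safety measures get subject-level counts:
- ESS (SAP 5.15.2): "The percentage of subjects with sleepy (10 or more) and very sleepy (18 or more) scores will also be summarized".
- Laboratory tests (SAP 5.15.5): shifts from baseline to worst value.
- Blood pressure and heart rate (SAP 5.15.6.1): subjects with out-of-range values.
- C-SSRS (SAP 5.15.9 and 9.4): treatment-emergent categories.

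Protocol 5.2, exclusion 5, removes "Subjects with a history or current diagnosis of a clinically significant impulse control disorder". Protocol 2.1 lists the D2/D3-agonist harms that tavapadon is meant to reduce: "notably, dose-limiting hypotension, impulse control disorders, sleep disorders, and, potentially, some forms of hallucinations".

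**The concern.** With existing cases excluded, the harm of interest is new onset. That would probably show as a large rise in one disorder in a minority, with most subjects near baseline. The MMRM tests something else: whether mean total ICD scores are equal. Averaging over all subjects, and adding the affected disorder to others that have not changed, shrinks the signal. The Section 5.9.2 model also takes its contrast at the endpoint visit under missing at random, so a peak that resolves, or that leads to withdrawal, gets little direct weight.

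Avoiding impulse-control harm is part of the drug's rationale. A null result from the only test on the instrument collected for this purpose could be given more weight than it deserves, and the plan offers no by-arm rate from that instrument to set beside it.

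**Working it through.** **The plan's own figure.** SAP 1.2 states "A sample size of 184 subjects per group (total, 368 subjects) will provide at least 90% power" for "1 hour with a standard deviation of 2.5" hours, with "a 2 sided alpha level = 0.049, and assuming a 27% dropout rate". Per arm, n = 2 × (1.969 + 1.282)² × 2.5² / 1² = 132.1, so 133. Then 133 / 0.73 = 182.2, so 183, against 184 planned. SAP Table 5 has 270 completers, or 135 per arm; the noncentral t gives 90.4%, 77.6% and 53.1% power at SD 2.5, 3.0 and 4.0, as the table states. No power is stated for the QUIP-RS. Below, 135 and 184 per arm bracket the information available to the MMRM.

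**Assumed inputs (none is in the documents).** s is the SD of change in total ICD score among unaffected subjects, r the rise in an affected subject, and e the excess proportion affected on tavapadon. Alpha is 0.05, two-sided.

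**Mean test, closed form.** The mean difference is e × r. The average SD is σ = √(s² + e(1 − e)r²/2). Power is Φ(e·r / (σ√(2/n)) − 1.96). With s = 5, r = 10 and e = 5%:
- difference 0.05 × 10 = 0.5; σ = √(25 + 0.0475 × 100 / 2) = 5.23
- n = 135: SE = 5.23 × √(2/135) = 0.637, ratio 0.785, power 12%
- n = 184: SE = 0.545, ratio 0.917, power 15%

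Across s = 3-7 and r = 6-15:

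| Excess e | Power, 135 per arm | Power, 184 per arm |
|---|---|---|
| 2% | 3-11% | 4-14% |
| 5% | 5-37% | 6-48% |
| 8% | 8-66% | 9-79% |
| 15% | 18-97% | 23-99% |

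**Count, perfect classification.** With a placebo rate of 1-5%, comparing proportions has 34-61% power (135 per arm) or 44-74% (184) at 5% excess, and 63-86% or 77-94% at 8%. At 2% excess it is also weak: 10-22% or 12-28%.

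**Count, with chance crossings generated.** Perfect classification flatters the count, so the rule itself was simulated: 184 per arm, four components, nine post-baseline visits, 27% dropout, 1% affected on placebo, r = 8-12. A subject counts if the worst post-baseline rise in any component is 8 or more.

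| SD of change | 5% affected: mean vs count | 8% affected: mean vs count |
|---|---|---|
| 3 | 12-17% vs 50-57% | 26-41% vs 85-91% |
| 4 | 9-14% vs 43-50% | 17-32% vs 79-87% |
| 5 | 8-11% vs 22-27% | 14-21% vs 45-59% |

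At SD 7 the ranges over both rates are 6-14% vs 6-15%. Repeat runs with slightly different settings, extended to SD 2, agree to within a few points: about 7-56% for the mean test and 23-92% for the count over SD 2-5.

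**Choice of cut-off.** Take component SD as half the total SD, independent components and visit-to-visit correlation of 0.5-0.8. The share of unaffected subjects who cross 4 points by chance is then about 1% at SD 2, 11-19% at SD 3, 36-53% at SD 4 and 80-91% at SD 7. At SD 4 with 8% vs 1% affected, the 4-point count has 9-12% power, below the mean test's 18-28%. At 8 points, chance crossing reaches 19-30% only at SD 7.

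**The case against.** The strongest reply is that the rest of the plan can show these cases.
- The descriptive summaries are not only means. Quartiles and the maximum are reported for each component, visit and arm, so a single large rise would be visible, and the listing shows whose it is.
- QUIP-RS is collected at early termination and mapped to a visit (SAP 9.2 and 4.2). The MMRM uses all visits to Week 27, so early scores can inform the Week 26 estimate. The simulated comparison of means at Week 26 does not credit this.
- An adverse event leading to discontinuation is an AESI with a narrative (Protocol 8.4.6.3) and has its own by-arm summary (SAP 5.15.1).
- SAP 5.15.1 tabulates TEAEs by preferred term, with extra tables for terms at 2% or more and above placebo, and at 5% or more and over twice placebo. An 8% vs 1% difference reported under one term would enter both.
- The documents give ESS thresholds but none for the QUIP-RS, so any cut-off is a new choice.

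All of this stands, and it limits the point. It does not remove it. Maxima and listings give no rate by arm. TEAEs rest on what staff observe or subjects volunteer to open-ended questions (Protocol Schedule of Assessments, footnote n, and 8.4.2), not on the questionnaire. The closed form at 184 per arm, which assumes no information is lost to dropout, still gives only 15% and 30% in the middle case at 5% and 8% excess. The lack of a documented threshold is a reason to fix one in advance.

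A reader might infer that the mean test is nearly blind to impulse-control harm. The figures do not support that: at 15% excess, still a minority, its power reaches 97-99% in the most favourable case. A reader might also infer that the sponsor will cite a non-significant MMRM as proof of no effect. No passage says so; the analysis is labelled exploratory, and SAP 5.1 reserves testing for efficacy endpoints.

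**Conclusion.** The gap is real and confined to the QUIP-RS analysis. The plan has no by-arm count of new or worsened impulse-control problems, and its single test compares means of a score it does not define. With 5-8% vs 1% affected, rises of 8-12 points and SD 2-5, power is roughly 7-56% for the mean test and about 23-92% for a count at 8 or more. At SD 7 neither is useful for testing, and at a 2% excess neither has adequate power. These figures rest wholly on assumed SDs, rates and rises, and on harm concentrated in one disorder. The documents do not support the broader inference that the trial's safety plan would miss an impulse-control signal. This is a cheap improvement to one section.

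**What to change.** In SAP 5.15.3 add one by-arm table on the safety set: the number and percentage of subjects whose worst post-baseline score in any of the four ICD components, at any visit including early termination, rises from baseline by a pre-specified amount. Show it by component and for any component, with the tavapadon minus placebo risk difference and 95% CI. The interval has value even where power is low, because it shows what excess cannot be excluded.

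Use a high cut-off, such as 8 or more on the 0-16 component scale, chosen before unblinding from blinded pooled data so that chance crossings are rare. Do not rely on 4 or more, which chance crossings can swamp. Define the total ICD score. Keep the MMRM as a description of mean change, and state that its non-significance is not evidence of no effect on impulse control.

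The cost is one SAP paragraph and one table from data already collected at baseline and every treatment visit. The downside is that the cut-off must be agreed before unblinding, and some subjects in both arms will cross it by chance.
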